3.2.4 Primary endpoint for secondary population

3.2.4.1 Definition of endpoint(s)

For the secondary population, the primary endpoint is Plasma and CSF GL-1 biomarker and pathway specific biomarkers, as shown in [Table 7](#).

Table 7 - Disease specific biomarkers for the secondary population

Disease	Biomarker
GM2 gangliosidosis	GL-1, GM2
GM1 gangliosidosis	GL-1, GM1
Sialidosis	GL-1, GM2, GM3
Galactosialidosis	GL-1, GM1, GM3
Saposin C Deficiency	GL-1 only

3.2.4.2 Main analytical approach

Primary endpoints in the secondary population will be summarized descriptively. Percent change from baseline in plasma and CSF GL-1 biomarker will be described for the entire secondary population. The pathway specific biomarker will be described separately for each disease in the secondary population. When at least 5 participants have available data in the entire secondary population or within a specific disease, a 95% confidence interval for the percent change from baseline will be provided. In addition, biomarker data will be summarized descriptively with individual plots and listings. No formal comparison will be performed in the secondary population.

The number and percentage of participants with values <LLOQ or >ULOQ will also be presented.

3.3 SECONDARY EFFICACY ENDPOINT(S) ANALYSIS

3.3.1 Primary population

3.3.1.1 Definition of endpoint(s)

Secondary efficacy endpoints include:

- Absolute change in CSF GM2 biomarker from baseline to week 104.
- Change in 25-foot walk test (25FWT) from baseline to Week 104 (in participants able to walk at baseline).
- Change in the neurological examination of the Friedreich's Ataxia Rating Scale (FARS-neuro) from baseline to Week 104.

3.3.1.2 Main analytical approach

3.3.1.2.1 Absolute change in CSF GM2

The endpoint of absolute change in CSF GM2 biomarker will be analyzed with the same approach used for percent change and described in [Section 3.2.1.2](#).

3.3.1.2.2 Change in 25FWT

The 25FWT will be derived from the two trials (see [Section 5.5.2](#) for derivation of the 25FWT).

Change in 25FWT will be analyzed only in participants able to walk at baseline. Participants unable to complete the 25FWT at baseline will be excluded from this analysis. To ensure balanced randomization of subjects able to walk at baseline, the randomization will be stratified based on the participant's ability to walk at the baseline visit.

Change in 25FWT will be compared between venglustat and placebo using a linear mixed-effect model with random intercept and slopes, similar to the analysis of the 9-HPT (see [Section 3.2.2.2](#)). The model will assume linear change over time in 25FWT after log transformation. The logarithm transformation was selected due to anticipated non-normal distribution of the 25FWT. A logarithm transformation will allow interpretation in terms of relative increase in time to complete the 25FWT (annual % increase per year).

Slope on venglustat and on placebo will be estimated from the linear mixed effect model. Efficacy of venglustat will be based on the comparison of slopes. The difference in slopes will be estimated and presented with its associated 90% confidence interval and p-value. Significance level will be the same as for the primary endpoint.

In case of outliers, the linear mixed-effect model will be replaced by the robust ANCOVA on individual slopes, described in [Section 3.2.2.3.1](#). The exact criterion to determine whether the robust ANCOVA should be used is presented in [Section 5.6.1.2](#).

3.3.1.2.3 Change in FARS-neuro

The FARS neurological score will be derived from the 23 items of the FARS-neuro (see [Section 5.5.3](#) for the derivation of the score).

Change in FARS-neuro will be compared between venglustat and placebo using a linear mixed-effect model with random intercept and slopes, similar to the analysis of the 9-HPT (see [Section 3.2.2.2](#)). The model will assume linear change over time in the FARS-neuro. No logarithm transformation will be performed for FARS neurological score.

Slope on venglustat and on placebo will be estimated from the linear mixed effect model. Efficacy of venglustat will be based on the comparison of slopes. The difference in slopes will be estimated and presented with its associated 90% confidence interval and p-value. Significance level will be the same as for the primary endpoint.

In case of outliers, the linear mixed-effect model will be replaced by the robust ANCOVA on individual slopes, described in [Section 3.2.2.3.1](#). The exact criterion to determine whether the robust ANCOVA should be used is presented in [Section 5.6.1.2](#).

3.3.1.3 Sensitivity analyses

The sensitivity analyses described in [Section 3.2.2.3](#) will also be conducted for the two secondary endpoints of 25FWT and FARS-neuro.

Since the log transformation is not applied for the FARS-neuro, sensitivity to the log transformation will not be conducted for this endpoint.

In addition, a sensitivity analysis of the FARS-neuro will be conducted, using the muscle weakness of triceps and quadriceps. In this sensitivity analysis, the score from the two items “Muscle Weakness - Right side” and “Muscle Weakness - left side” from the Peripheral Nervous System section of FARS-neuro (see [Table 15](#) for details) will be replaced by the scores from the muscle weakness of triceps and quadriceps (right and left side).

The sensitivity analyses described in [Section 3.2.1.3](#) will also be conducted on absolute change in CSF GM2 biomarker endpoint.

3.3.1.4 Supportive analyses

Time to meaningful worsening in 25FWT and in FARS-neuro will be conducted, using the method described in [Section 3.2.2.4.3](#).

Time to meaningful improvement in 25FWT and in FARS-neuro will be conducted, using the method described in [Section 3.2.2.4.4](#).

Descriptive analysis will be conducted on 25FWT and FARS-neuro, using the method described in [Section 3.2.2.4.5](#).

3.3.1.5 Subgroup analyses

The subgroup analyses described in [Section 3.2.3](#) will also be conducted for the three secondary endpoints presented above.

3.3.2 Secondary population

3.3.2.1 Definition of endpoint(s)

- Annualized rate of change in the 9-HPT from baseline to Week 104.
- Change in 25FWT from baseline to Week 104 (in participants able to walk at baseline).
- Change in the FARS-neuro from baseline to Week 104.

3.3.2.2 Main analytical approach

Secondary endpoints in the secondary population will be summarized descriptively with individual plots and listings. When at least 5 participants have available data at baseline and Week 104, mean change from baseline to Week 104 will be provided with 95% confidence interval. No formal comparison will be performed in the secondary population.

For the descriptive analysis of 9-HPT, participants with maximum score (300 seconds) at baseline or unable to complete the test at baseline will be excluded.

Similarly, for the descriptive analysis of 25FWT, participants with maximum score (180 seconds) at baseline or unable to complete the test at baseline will be excluded.

[figure not shown]
Number and percentage of participants who did not complete the assessments will be described by time point.

3.4 TERTIARY/EXPLORATORY EFFICACY ENDPOINT(S) ANALYSIS

The analysis will be conducted in two steps (see [Section 3.8.2](#)). The exploratory endpoints at Week 104 will be presented in the first step analysis. The exploratory endpoints at Week 208 will be presented in the second step analysis.

The exploratory efficacy endpoints are the same for the primary and secondary populations.

3.4.1 Definition of endpoint(s)

[figure not shown]

3.4.2 Main analytical approach

For all exploratory efficacy endpoints, the analyses will be descriptive, and no testing are planned. Continuous data will be summarized by treatment group using the number of observations available, mean, standard deviation (SD), median, [Q1, Q3], minimum, and maximum. Categorical and ordinal data will also be summarized by treatment group using the count and percentage of participants. If applicable the change and percent change from baseline will be presented.

3.4.2.1 [REDACTED]

3.4.2.2

3.4.2.3

3.4.2.4

3.4.2.5

Table 8 -

A series of horizontal black bars of varying lengths, likely representing data points or categories in a bar chart. The bars are arranged in several groups, with some groups having a single bar and others having multiple bars. The lengths of the bars vary significantly, with some being very short and others being very long.

A horizontal bar chart illustrating the distribution of 1000 random numbers. The x-axis represents the value of the random numbers, ranging from 0 to 1. The y-axis represents the frequency of each value, with 1000 bars. The distribution is approximately uniform, with most values falling between 0.4 and 0.6. The bars are black and have thin white outlines.

Value Range	Frequency
0.0 - 0.1	~100
0.1 - 0.2	~100
0.2 - 0.3	~100
0.3 - 0.4	~100
0.4 - 0.5	~100
0.5 - 0.6	~100
0.6 - 0.7	~100
0.7 - 0.8	~100
0.8 - 0.9	~100
0.9 - 1.0	~100

3.5 MULTIPLICITY ISSUES

No adjustment for multiplicity will be considered for the co-primary endpoints (percent change in CSF GM2 from baseline to Week 104 and annualized rate of change in 9-HPT) since it will be necessary to demonstrate an effect on both co-primary endpoints to conclude to efficacy.

In order to handle multiple secondary endpoints, the overall type-I error will be controlled by the Hochberg procedure. Statistical significance of the two co-primary endpoints is required before drawing inferential conclusions about secondary endpoints.

No further adjustments will be made for exploratory endpoints for which p-values may be provided for descriptive purpose only.

3.6 SAFETY ANALYSES

All safety analyses will be performed on the safety populations as defined in [Section 2](#) for the two steps analysis, unless otherwise specified, using the following common rules:

- The analysis of the safety variables will be essentially descriptive, and no testing is planned.
- Safety data in participants who do not belong to the safety population (eg, exposed but not randomized) will be provided separately if any.

In the first step analysis, safety data will be presented for the following period:

- Safety analysis of the primary analysis period. This analysis will present safety data collected during the primary analysis period (as defined in [Section 3.1](#)). Safety analyses will present safety data in the following arms:
 - Primary population – Placebo: participants from the primary population, having received placebo during the primary analysis period.
 - Primary population – Venglustat: participants from the primary population, having received venglustat during the primary analysis period.
 - Secondary population – Venglustat: participants from the secondary population, having received venglustat during the primary analysis period.

In the second step analysis, safety data will be presented separately for the two following periods:

- Safety analysis of the OLE period. This analysis will present safety data collected during the OLE period (as defined in [Section 3.1](#)). Only participants having received venglustat during the OLE period will be included in this analysis. Safety analyses will present safety data from the following groups:
 - Primary population - Delayed venglustat: participants from the primary population, having received placebo during the primary analysis period, then having received venglustat during the OLE period.
 - Primary population - Early venglustat: participants from the primary population, having received venglustat during the primary analysis period, then having continued to receive venglustat during the OLE period.

- Primary population - All venglustat: all participants from the primary population having received venglustat during the OLE period.
- Secondary population – Venglustat: participants from the secondary population having received venglustat during the OLE period.
- Safety analysis of the overall venglustat treatment period. This analysis will present adverse event occurring from the first intake of venglustat to the last intake of venglustat plus 6 weeks. All participants having received venglustat (either during the primary analysis period or during the OLE period) will be included in this analysis. Safety analyses will present safety data from the following groups:
 - Primary population - Venglustat: participants from the primary population having received venglustat during the primary analysis period and/or during the OLE period.
 - Secondary population - Venglustat: participants from the secondary population having received venglustat during the primary analysis period and/or during the OLE period.
 - All - Venglustat: all participants from the primary or secondary population, having received venglustat during the primary analysis period and/or during the OLE period.

3.6.1 Extent of exposure

The extent of IMP exposure will be assessed for the two steps analysis by the duration of IMP exposure and compliance and summarized within the safety populations.

Duration of IMP exposure

Duration of IMP exposure is defined as last IMP administration date – first IMP administration date +1 day, regardless of unplanned intermittent discontinuations. If the date of the last dose of IMP is missing, the duration of IMP will be left as missing.

The duration is defined differently for the two steps of the analysis (see [Section 3.8.2](#)):

Duration of IMP exposure for the primary analysis period is defined as:

- The last IMP administration date during the primary analysis period - first IMP administration date +1.

Duration of IMP exposure for the OLE period is defined as:

- The last IMP administration date during the OLE period - first IMP administration date during the OLE period +1 day.

In addition, overall duration of exposure to venglustat is defined as:

- The last venglustat administration date (either during the primary analysis period or OLE period) - first IMP administration date (either during the primary analysis period or OLE period) +1 day.

Duration of IMP exposure will be summarized quantitatively and categorically:

- ≥ 1 day.
- ≥ 4 weeks (1 month).
- ≥ 12 weeks (3 months).
- ≥ 26 weeks (6 months).
- ≥ 52 weeks (12 months).
- ≥ 78 weeks (18 months).
- ≥ 104 weeks (24 months).
- ≥ 130 weeks (30 months).
- ≥ 156 weeks (36 months).
- ≥ 182 weeks (42 months).
- ≥ 208 weeks (48 months).

Additionally, the cumulative duration of treatment exposure (expressed in participant-years) will be provided.

Summary of extent of exposure will be provided for the safety population as well as for the population with trial impact (disruption) due to COVID-19.

Treatment compliance

A given administration will be considered noncompliant if the participant did not receive the number of days of IMP as required by the protocol. No imputation will be made for participants with missing or incomplete data.

Percentage of treatment compliance for a participant will be defined as the number of days of IMP administered divided by the total number of days that the participant was planned to take from the first administration of IMP up to the actual last administration of IMP.

Treatment compliance will be summarized quantitatively and categorically: $<80\%$, $\geq 80\%$.

Cases of overdose are reported in the adverse event (AE) e-CRF pages as Adverse Event of Special Interest (AESI) if symptomatic or AE if asymptomatic. The reported cases of overdose will be described in the AE analysis (see [Section 3.6.2](#)).

Acceptability and palatability

For pediatric secondary population, the acceptability and palatability of venglustat tablets will be assessed for the two steps analysis by the route of venglustat administration collected in the eCRF and the treatment compliance (as defined in the above section).

Treatment compliance of participants from the pediatric secondary population will be summarized quantitatively and categorically ($<80\%$, $\geq 80\%$) according to the route of venglustat administration (Swallowed the Tablet as Whole, Chewed and Swallowed) within the secondary safety population.

[REDACTED]

[REDACTED]

[REDACTED]

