Disclosure Statement: This is a Parallel, Treatment study with 2 arms that are blinded/masked for Investigator and participants in the primary population for the primary analysis at 104 weeks. For the secondary population, this is an open-label, single-arm treatment study.

Number of participants:

Approximately 57 participants with late-onset adult GM2 gangliosidosis will be treated in the study (primary population). After safety data from Week 1/Day 1 to Week 12 visits for the first 5 participants of the primary population are reviewed and considered satisfactory, enrollment of the secondary population will begin. In addition to the primary population, up to 20 participants in total are planned for the secondary population. An attempt will be made and first prioritized to enroll at least 1 participant (age 2 years or older) in each of the following disorders: juvenile/adolescent late-onset GM2 gangliosidosis, GM1 gangliosidosis, Saposin C deficiency, Sialidosis Type 1, and juvenile/adult galactosialidosis.

Intervention groups and duration:

During the 104-week primary analysis treatment period, participants in the primary population will be randomly assigned in a 2:1 ratio to receive venglustat or placebo once daily in a double-blind manner. Randomization will be stratified on the participant's ability to walk at the baseline visit (yes/no). Participants in the secondary population will receive venglustat for 104 weeks in an open-label manner.

During the 104-week OLE treatment period, all participants in both primary and secondary populations will receive venglustat in an open-label manner.

Study intervention(s)

Investigational medicinal products: Venglustat or placebo

- Formulation: venglustat [REDACTED] and 15 mg and placebo (identical to venglustat 15 mg tablets in appearance) tablets. The placebo is only for 15 mg venglustat tablets. Strength refers to the free base corresponding to the active moiety.
- Route of administration: oral.
- Dose regimen:
 - The investigational medicinal product (IMP) can be swallowed whole or chewed and then swallowed. Administration of IMP by chewing and swallowing or swallowing whole should be as consistent as possible throughout study treatment, and the method should be documented in the electronic case report form.

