- **The on-treatment period** is defined as the time from the first administration of IMP to the last administration of IMP in the primary analysis period +1 day (including any temporary treatment discontinuation period, if any).
- **The residual treatment period**, if any is defined as the time from the end of the on-treatment period to the end of the TE period.
- **The post-treatment period** is defined as the period starting the day after the end of the TE period, up to the end of the primary analysis period.

During the **OLE period** (as defined above), the following observation periods are defined:

- **The treatment-emergent (TE) period** is defined as the time from the start of the OLE period to the last administration of the OLE IMP +6 weeks (including any temporary treatment discontinuation period, if any).

The TE period includes the following 2 periods:

- **The on-treatment period** is defined as the time from the start of the OLE period to the last administration of the OLE IMP +1 day (including any temporary treatment discontinuation period, if any).
- **The residual treatment period** is defined as the time from the end of the on-treatment period to the end of the TE period.
- **The post-treatment period** is defined as the period starting the day after the end of the TE period up to the end of the study.

In addition, the overall venglustat treatment-emergent period will combine the primary analysis period and the OLE period:

- The **overall venglustat treatment-emergent period** is defined as the time from the first intake of venglustat to the last intake of venglustat +6 weeks (including any temporary treatment discontinuation period, if any). Depending on the treatment received during the primary analysis period (venglustat or placebo), the first intake of venglustat may be either during the primary analysis period or during the OLE period.

The on-study observation period is defined as the time from the first administration of the IMP until the end of the study (defined as the last scheduled visit for those who completed the study and the end-of-study date collected on electronic case report form (e-CRF) page “Completion of End of Study” for those who did not complete the study. If death is the end-of-study reason, date of death will be used.

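### Overall venglustat exposure is counted from the first IMP dose, so placebo time is included for placebo participants who enter the extension

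*SAP*

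**What the plan says.** SAP 3.6.1 gives separate exposure durations for the primary analysis period and the OLE, then adds an overall duration of exposure to venglustat. That duration ends at the last venglustat date in either period. It starts at the "first IMP administration date (either during the primary analysis period or OLE period) +1 day".

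The Protocol synopsis defines the term: "Investigational medicinal products: Venglustat or placebo". Table 4 in Protocol 6.1 likewise lists both arms as IMP.

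Two companion passages use a different start:

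- SAP 3.1 runs the overall venglustat treatment-emergent period from the first venglustat dose and adds that "the first intake of venglustat may be either during the primary analysis period or during the OLE period", depending on the treatment received in the primary period.
- SAP 3.6 says that the second-step overall venglustat analysis covers "adverse event occurring from the first intake of venglustat to the last intake of venglustat plus 6 weeks".

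SAP 3.6 also names the participants concerned, the delayed-venglustat group, as those "having received placebo during the primary analysis period, then having received venglustat during the OLE period". Their OLE-period duration is defined without difficulty: "The last IMP administration date during the OLE period - first IMP administration date during the OLE period +1 day".

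On outputs, SAP 3.6.1 says that "Duration of IMP exposure will be summarized quantitatively and categorically", with rows from at least 1 day to at least 208 weeks, and that "the cumulative duration of treatment exposure (expressed in participant-years) will be provided".

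**The concern.** The end date of the overall duration is specific to venglustat but the start date is not. Under Protocol 4.1, participants enter the OLE only after completing the primary analysis period, so their first IMP dose always falls in that earlier period. For a placebo starter that dose is placebo. Programmed as written, the line adds about 104 weeks of placebo to that person's venglustat exposure, plus any time off drug before the OLE.

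At stake is the overall venglustat exposure summary in the second step: the mean duration, the long-duration rows and, if they use this definition, the participant-years. For placebo starters the exposure and the adverse-event window of the same analysis would begin about two years apart. The overall exposure would also disagree with the OLE-period exposure for the same people. The SAP plans no event rates per participant-year, but any rate later built on these totals would be too low.

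**Working it through.** **Inputs.** Planned sizes are 38 venglustat and 19 placebo (SAP 4), with up to 20 in the secondary population, all on venglustat (SAP 1.1). Each period lasts 104 weeks. Week 104 is Day 728 and Week 208 is Day 1456 (SAP Table 13). The first OLE dose is taken the day after the Visit 7 assessments (Protocol 1.3), so Day 729 is used. The plan states no exposure figure to reproduce.

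**One placebo starter who completes the OLE.**

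- As worded: 1456 − 1 + 1 = 1456 days = 208 weeks.
- From first venglustat: 1456 − 729 + 1 = 728 days = 104 weeks.

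**Participant-years.** Take 2 years per period, everyone completing the primary period, and the same OLE uptake *p* in both arms. Placebo participants who never enter the OLE contribute nothing under either rule.

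- True total, primary population: 38×2 + 38×2*p* + 19×2*p* = 76 + 114*p*.
- Excess under the literal rule: 19×2*p* = 38*p*.
- Adding 20 secondary participants adds 40 + 40*p* to the true total and nothing to the excess.

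| OLE uptake | Primary: literal vs true | Excess | With secondary: literal vs true | Excess |
|---|---|---|---|---|
| 100% | 228 vs 190 | 38 (+20.0%) | 308 vs 270 | +14.1% |
| 75% | 190.0 vs 161.5 | 28.5 (+17.6%) | 260.0 vs 231.5 | +12.3% |
| 50% | 152 vs 133 | 19 (+14.3%) | 212 vs 193 | +9.8% |

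At full uptake the mean is 228/57 = 4.0 years against 190/57 = 3.3. Using days divided by 365.25 instead, the primary totals are 227.2 against 189.3, again +20%.

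**With dropout.** The SAP simulation code (5.6.3.3) uses 10% dropout by year 2. As an assumption, apply that to treatment, continue it to year 4, and let everyone remaining enter the OLE.

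- Hazard: *h* = −ln(0.9)/2.
- Mean time on treatment: 1.898 years in years 0–2, and 0.9 × 1.898 = 1.708 in years 2–4.
- True primary total: 38 × (1.898 + 1.708) + 19 × 1.708 = 169.5.
- Excess: 19 × 0.9 × 2 = 34.2. Literal total: 203.7 (+20.2%).
- With 20 secondary participants: 275.8 against 241.6 (+14.2%).

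**Duration rows, if they use this duration.** With full retention and 104 OLE weeks each, rows up to 104 weeks do not change. All 19 placebo starters appear wrongly in each of the rows for at least 130, 156, 182 and 208 weeks. Under the dropout assumption, the 104-week row holds 19 × 0.9 = 17.1 placebo starters against a true 19 × 0.81 = 15.4, and the 208-week row holds 15.4 against 0. A placebo starter who stops after 20 OLE weeks is recorded at 104 + 20 = 124 weeks and wrongly enters the rows for at least 26, 52, 78 and 104 weeks.

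**Gap before the OLE.** Protocol 4.1 lets participants who finished within 3 months before local approval of the OLE join once it was approved. An assumed gap of 0.25 year adds up to 19 × 0.25 = 4.75 participant-years if all 19 are affected and none if no one is. The number affected is not stated.

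**The case against.** The strongest reply is that the documents already show what was meant. The quantity is named for venglustat and its end date is a venglustat date. The bracketed reference to either period is empty unless the start is also a venglustat date, because no one's first IMP dose can fall in the OLE. SAP 3.1 and 3.6 point the same way. All of this stands as evidence of intent. It does not change the line that a programmer would follow.

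Second, the SAP attaches the categories to IMP exposure and the participant-years to treatment exposure, not to the overall venglustat duration. The section also opens with a general last-IMP-minus-first-IMP definition. Read as spanning both periods, that could fill the rows above 104 weeks and would correctly place a placebo starter at 208 weeks of IMP. This is fair. The link from the faulty line to those rows and to the participant-years is an inference. The SAP then defines duration differently for each step, and the overall venglustat duration is the only combined-period one it names after that. The error in the duration itself does not depend on the inference.

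Third, the simulation's dropout parameter describes loss of 9-HPT observations, not stopping treatment. The 3-month gap is not a cap either, because entry follows approval. Both limit those scenarios, which serve only as illustrations. A gap in the original venglustat arm would also remain counted after the correction.

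Finally, the correct exposure for placebo starters is available from the OLE-period analysis, so an error could be noticed. That is a reason for low severity.

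**Conclusion.** The point holds as a minor one. Followed as written, the definition counts placebo time as venglustat exposure for every placebo participant who goes on to take venglustat, and it contradicts the SAP's own start of the overall venglustat period.

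The individual error is about 104 weeks. At planned sizes, and if participant-years are built on this duration, the primary-population total is overstated by 14% to 20% for OLE uptake between 50% and 100%. The pooled total is overstated by about 10% to 14%. All totals are scenarios that assume literal programming.

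Efficacy, first-step exposure, OLE-period exposure and the planned adverse-event numbers and percentages are not touched. Nor are the original venglustat arm or the secondary population taken alone, since their first IMP dose is venglustat.

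**What to change.** In the overall-duration line of SAP 3.6.1, replace the first IMP administration date with the first venglustat administration date, in either period. Add one sentence saying that this overall duration is the one used for the duration categories and the cumulative participant-years in the overall venglustat analysis. The cost is one phrase and one sentence in the SAP before the second-step analysis. No new data are needed.
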